5.3.5 Cycle 1 Medications

Cycle 1 Day 1:

- A 5 to 28-day supply of venetoclax at the appropriate dose level will be distributed to the subject.
- 14 doses (28-day supply) of CC-486 at the appropriate dose level will be distributed to the subject.
- Obinutuzumab 1000 mg IV (dose-finding cohort only).

Cycle 1 Day 8:

• Obinutuzumab 1000 mg IV (dose-finding cohort only)

Cycle 1 Day 15:

• Obinutuzumab 1000 mg IV (dose-finding cohort only)

Cycle 1 Day 22: No facility-administered medications

5.4 CYCLE 2 AND 3 VISITS

There will be three study visits during Cycles 2 and 3. Each subject will be assessed and/or treated in the clinic at the appropriate study site on Day 1 and Day 15 during Cycle 2 and on Day 1 only during Cycle 3. Visits should ideally occur exactly on the scheduled date but are permitted to be rescheduled within a window of \pm days.

5.4.1 Cycle 2-3 Methods and Procedures

Cycle 2 and 3 visits will take place in the oncology clinic space at participating trial sites. A focused medical history will be obtained and recorded in the clinical record by the treating investigator or qualified designee, as well as any changes in concomitant medical conditions, current medications, allergies, or social history. Current symptoms will be elucidated and recorded in the clinical record.

5.4.2 Cycle 2-3 Scales and Assessments

The treating investigator or qualified designee will take vital signs including temperature, pulse, respiratory rate, weight and blood pressure. The body mass index (BMI) and body surface area (BSA) will be calculated.

- The treating investigator or qualified designee will assess ECOG status (Appendix B) at each visit.
- A blood sample for correlative studies is to be provided to the main University of Chicago site for circulating methylation profiling (see Section 5.10) on Cycle 3 Day 1 only.

5.4.3 Cycle 2-3 Examinations and Questionnaires

The treating investigator or qualified designee will perform a focused physical exam during each visit. Clinically significant abnormal findings should be recorded as medical history. The treating investigator or qualified designee may use standard intake forms to facilitate the collection of changes in medical history, and medication list. These must be verified in a face-to-face encounter. No additional questionnaires are required.

5.4.4 Cycle 2-3 Laboratory Studies

On Day 1 (both Cycle 2 and 3) and Day 15 (Cycle 2 only), the following studies should be obtained and reviewed prior to administration of any treatment scheduled for that day:

• Complete blood count (CBC) with differential counts including hemoglobin, hematocrit, red blood cell count, mean corpuscular volume, white blood cell count, platelet count, absolute

- and relative neutrophil count, absolute and relative lymphocyte count, absolute and relative monocyte count, and absolute and relative eosinophil count.
- Complete metabolic panel including serum glucose, sodium, potassium, chloride, bicarbonate, blood urea nitrogen, creatinine, total protein, albumin, alanine transaminase, aspartate transaminase, and alkaline phosphatase.
- Serum lactate dehydrogenase level.
- Serum uric acid level on Day 1 only, repeat as needed (see Appendix G).
- Serum beta-2 microglobulin level on Day 1 only.

5.4.5 Cycle 2-3 Medications

Cycle 2 Day 1:

- A 5 to 28-day supply of venetoclax at the appropriate dose level will be distributed to the subject.
- 14 doses (28-day supply) of CC-486 at the appropriate dose level will be distributed to the subject.
- Obinutuzumab 1000 mg IV (dose-finding cohort only)
- TLS prophylaxis may be continued, restarted or discontinued after Cycle 1 is completed per the judgment of the treating investigator.

Cycle 2 Day 15: no facility-administered medications

Cycle 3 Day 1:

- A 5 to 28-day supply of venetoclax at the appropriate dose level will be distributed to the subject
- 14 doses (28-day supply) of CC-486 at the appropriate dose level will be distributed to the subject.
- Obinutuzumab 1000 mg IV (dose-finding cohort only)

5.5 CYCLE 4 VISITS

Patients will be assessed and/or treated in the clinic at the appropriate study site on the following days during the 28-day Cycle 4:

- Day 1
- Day 8 (expansion cohort only)
- Day 15 (expansion cohort only)

5.5.1 Cycle 4 Methods and Procedures

Cycle 4 visits will take place in the oncology clinic space at participating trial sites. A focused medical history will be obtained and recorded in the clinical record by the treating investigator or qualified designee, as well as any changes in concomitant medical conditions, current medications, allergies, or social history. Current symptoms will be elucidated and recorded in the clinical record.

5.5.2 Cycle 4 Scales and Assessments

The treating investigator or qualified designee will take vital signs including temperature, pulse, respiratory rate, weight and blood pressure. The body mass index (BMI) and body surface area (BSA) will be calculated.

- The treating investigator qualified designee will assess ECOG status (Appendix B) at each visit.
- Prior to the Cycle 4 Day 1 visit, the first interim PET imaging for disease response (secondary outcome assessment) must be completed. See Appendix E for details of PET interpretation and response assessment.

5.5.3 Cycle 4 Examinations and Questionnaires

The treating investigator or qualified designee will perform a focused physical exam during each visit. Clinically significant abnormal findings should be recorded as medical history. The treating investigator or qualified designee may use standard intake forms to facilitate the collection of changes in medical history, and medication list. These must be verified in a face-to-face encounter. No additional questionnaires are required.

5.5.4 Cycle 4 Laboratory Studies

On Day 1 (both dose-finding and expansion cohorts) and 8, and 15 (expansion cohort only), the following studies should be obtained and reviewed prior to administration of any treatment scheduled for that day:

- Complete blood count (CBC) with differential counts including hemoglobin, hematocrit, red blood cell count, mean corpuscular volume, white blood cell count, platelet count, absolute and relative neutrophil count, absolute and relative lymphocyte count, absolute and relative monocyte count, and absolute and relative eosinophil count.
- Complete metabolic panel including serum glucose, sodium, potassium, chloride, bicarbonate, blood urea nitrogen, creatinine, total protein, albumin, alanine transaminase, aspartate transaminase, and alkaline phosphatase.
- Serum lactate dehydrogenase level.
- Serum uric acid level on Day 1 only, repeat as needed (see Appendix G).
- Serum beta-2 microglobulin level on Day 1 only.

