The study design consists of two arms. First, in the dose-finding arm aimed at establishing a recommended phase 2 dose and uncovering dose limiting toxicities in a novel triplet combination therapy, all three investigational agents will be given together starting in cycle 1. This will allow early assessment of toxicity from the three-drug combination and efficient progression through dose levels in a standard "3 + 3" design.

In the expansion cohort, a "window" design will be used to explore the efficacy of the combination of venetoclax and CC-486 alone before obinutuzumab is added in cycle 4. The efficacy of anti-CD20 therapy in FL is already well-established, and this design will provide an opportunity to assess the effects of a novel two-drug combination independent of confounding effects of an agent known to be effective for many patients. To minimize the chance of exposing patients to a futile treatment, the expansion cohort will follow a Simon two-stage design for an interim assessment of efficacy based on response to the three-drug combination at 6 months. The study will be halted for futility if the criteria for early efficacy are not met.

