2.3 SCHEDULE OF EVENTS

For each study visit, basic information including body measurements and vital signs will be recorded. Symptoms of the disease and treatment-related toxicities will be collected and recorded by a licensed medical provider. A physical exam will be performed and documented by a licensed medical provider. Scheduled laboratory assessments will be drawn on the day of the appointment. The assessments and procedures conducted at each visit will follow the study schema shown in **Appendix A.**

The schedule will proceed as follows: first there will be a screening visit within 28 days prior to Cycle 1 to determine eligibility and review the protocol. A 28-day supply of venetoclax and 14-day supply of CC-486 will be given to the patient on Day 1 of each cycle. Cycle 1 will require visits on Day 1, 8, 15, and 22 for treatment, laboratory assessments, and assessment. In the dose-finding cohort only, infusional therapy with obinutuzumab will be given on Cycle 1 Day 1, Cycle 1 Day 8, and Cycle 1 Day 15 in the dose-finding arm. In the expansion cohort, no obinutuzumab will be given in Cycle 1, but the patient will be assessed for toxicity weekly.

Cycle 2 will require visits on Day 1 and Day 15. Infusional therapy with obinutuzumab will be given on Cycle 2 Day 1 in the dose-finding arm only. Cycle 3 through 12 will require visits on Day 1 only in the dose finding arm. The last dose of obinutuzumab will be given on Cycle 9 Day 1 in the dose finding arm. In the expansion cohort, obinutuzumab treatment will start in Cycle 4, with infusions and laboratory studies on Day 1, Day 8, and Day 15; subsequent Cycles through Cycle 12 will include an obinutuzumab infusion on Day 1 only. The end-of-treatment visit will occur within 4 weeks of completion of treatment on Cycle 12, Day 28. Follow-up visits will occur every 8-12 weeks until 18 months post-treatment, and every 6 months thereafter until the close of the trial or disenrollment of the patient.

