5.3.4 Cycle 1 Laboratory Studies

On Days 1, 8, 15, and 22, the following studies should be obtained and reviewed prior to administration of any treatment scheduled for that day:

- Complete blood count (CBC) with differential counts including hemoglobin, hematocrit, red blood cell count, mean corpuscular volume, white blood cell count, platelet count, absolute and relative neutrophil count, absolute and relative lymphocyte count, absolute and relative monocyte count, and absolute and relative eosinophil count.
- Complete metabolic panel including serum glucose, sodium, potassium, chloride, bicarbonate, blood urea nitrogen, creatinine, total protein, albumin, alanine transaminase, aspartate transaminase, and alkaline phosphatase.
- Serum lactate dehydrogenase level.
- Serum uric acid level on Day 1 only, repeat as needed (see Appendix G)
- Serum beta-2 microglobulin level on Day 1 only.

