5.6.4 Cycle 5-9 Laboratory Studies

On Day 1 of Cycles 5-9, the following studies should be obtained and reviewed prior to administration of any treatment scheduled for that day:

a) Complete blood count (CBC) with differential counts including hemoglobin, hematocrit, red blood cell count, mean corpuscular volume, white blood cell count, platelet count, absolute and relative neutrophil count, absolute and relative lymphocyte count, absolute and relative monocyte count, and absolute and relative eosinophil count.

- b) Complete metabolic panel including serum glucose, sodium, potassium, chloride, bicarbonate, blood urea nitrogen, creatinine, total protein, albumin, alanine transaminase, aspartate transaminase, and alkaline phosphatase.
- c) Serum lactate dehydrogenase level.
- d) Serum uric acid level.
- e) Serum beta-2 microglobulin level.

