7.4.4.1 Antimicrobial Prophylaxis

Previous studies have demonstrated a heightened risk for viral, fungal and bacterial infections with single agent and combination therapy using the agents under investigation in this protocol. This risk may be partially mitigated by the use of appropriate antimicrobial prophylaxis. The choice of agents and timing of prophylaxis are up to the clinical judgment of the treating physician. However, the following guidance and suggestions are provided for antimicrobial prophylaxis:

- There is low risk compared to significant possible benefit for acyclovir or valacyclovir antiviral prophylaxis. 400 mg acyclovir PO twice daily or equivalent dose is recommended for all patients undergoing active treatment from the screening visit until 6 months after the last dose of investigational agents, unless there is a competing risk.
- Patients with severe and long lasting (1 week) neutropenia are strongly recommended to receive antimicrobial prophylaxis until resolution of neutropenia to grade 1 or 2. The choice of prophylactic agent may be individualized within the current National Comprehensive Cancer Network guidelines (National Comprehensive Cancer Network 2017), and should be at least equivalent in coverage and potency to 500mg levofloxacin PO daily. Patients with transient or no neutropenia can be considered on a case-by-case basis for antibacterial prophylaxis based on the treating investigator's estimation of the baseline infection risk.
- Antifungal prophylaxis is complicated by drug-drug interactions between venetoclax and the azole class of antifungal agents. In prior studies in AML patients of hypomethylating agents such as azacitidine alone, the rate of invasive fungal infections in patients not on antifungal prophylaxis was 4.1% (Pomares et al. 2016), which rose to 8% Grade 3/4 fungal infections in AML patients treated with a combination of venetoclax and azacitidine (DiNardo et al. 2019). Complicating the assessment of this risk is that 46% of the patients on the latter trial received non-azole antifungal prophylaxis. Real-world analysis of patients treated with venetoclax for CLL showed lower rates of invasive fungal infection (1.4%) (Mato et al. 2018).
 - For this protocol, the following antifungal prophylaxis is recommended for all patients with Grade 3/4 neutropenia lasting longer than one week: 300 mg micafungin IV infusion three times per week (Muilwijk et al. 2018; Neofytos et al. 2015).

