7.4.5 Thrombocytopenia

Severe and life-threatening thrombocytopenia has been reported during treatment with obinutuzumab in combination with chlorambucil or bendamustine, and has also been reported with intravenous azacitidine in prior studies and in commercial use. Fatal hemorrhagic events during Cycle 1 have also been reported in patients with CLL treated with obinutuzumab. Cytopenias, including thrombocytopenia, are also a known risk of venetoclax and azacitidine in combination.

Monitor all patients frequently for thrombocytopenia and hemorrhagic events, especially during the first cycle of obinutuzumab administration. In patients with Grade 3 or 4 thrombocytopenia, monitor platelet counts more frequently until resolution and consider subsequent dose delays of obinutuzumab or dose reductions of oral investigational therapy per Section 4.2. Transfusion of blood products (i.e., platelet transfusion) may be necessary. Consider withholding concomitant medications which may increase bleeding risk (e.g. platelet inhibitors, anticoagulants), especially during the first cycle.

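### In the expansion cohort, scheduled blood counts lapse for 14 and then 28 days after obinutuzumab loading in Cycle 4, and the Day 2 TLS labs of 4.2.4 are missing from the schedule

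*Combined protocol and SAP*

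**What the plan says.** **Dose finding.** Section 1.1.7 states that "all three investigational agents will be given together starting in cycle 1". The first two triplet cycles are therefore Cycles 1 and 2. Section 5.3.4 sets the Cycle 1 labs, which include a CBC with differential: "On Days 1, 8, 15, and 22, the following studies should be obtained". Section 5.4.4 continues: "On Day 1 (both Cycle 2 and 3) and Day 15 (Cycle 2 only), the following studies should be obtained".

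**Expansion.** Section 4.2.1.2 omits obinutuzumab from Cycles 1-3 and gives it on Days 1, 8 and 15 of Cycle 4, then on Day 1 only. The first two triplet cycles are therefore Cycles 4 and 5. The Cycle 4 labs are set by 5.5.4: "On Day 1 (both dose-finding and expansion cohorts) and 8, and 15 (expansion cohort only), the following studies should be obtained". Section 5.6.4 follows with "On Day 1 of Cycles 5-9, the following studies should be obtained". Appendix A agrees: for expansion, the Day 22 column covers Cycle 1 only and the Day 15 column covers Cycles 1, 2 and 4.

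**Monitoring guidance.** Section 7.4.5 asks sites as follows: "Monitor all patients frequently for thrombocytopenia and hemorrhagic events, especially during the first cycle of obinutuzumab administration". Section 2.3 says of expansion that "no obinutuzumab will be given in Cycle 1, but the patient will be assessed for toxicity weekly".

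**TLS labs.** For expansion patients at TLS risk, 4.2.4 calls for labs on Days 1, 2, 8 and 15 when obinutuzumab starts. Section 7.4.1.1 leaves post-dose labs to the investigator and says the protocol does not require them. Section 5.5.4 and Appendix A have no Day 2.

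**The concern.** Expansion patients have weekly counts in Cycle 1 on two drugs, but no Day 22 count in Cycle 4, when the third drug is added. That is the cycle 7.4.5 singles out. Dose finding does not test loading obinutuzumab after three cycles of the oral doublet, so this sequence is new to the trial when expansion opens.

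What is at stake is the timely detection of a first, symptom-free grade 3-4 cytopenia. The holds for neutropenia and thrombocytopenia in Table 3A begin only once a count shows the event. Prophylaxis under 7.4.4.1 depends on duration: "antifungal prophylaxis is recommended for all patients with Grade 3/4 neutropenia lasting longer than one week", with similar advice on antibacterials for severe neutropenia of about a week. Grade 3-4 neutropenia, thrombocytopenia and anemia are also AESIs with expedited reporting (8.2.5, 8.3.2).

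The TLS point is separate. A site that works from the visit schedule would leave out a safety lab that 4.2.4 asks for.

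**Working it through.** **Inputs.** Cycle length is 28 days (2.4). CBC days are from 5.3.4, 5.4.4, 5.5.4, 5.6.4 and Appendix A. The plan states no figure of its own to reproduce.

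**Step 1: counts and gaps in the first two triplet cycles.** The last gap runs to Day 1 of the following cycle.

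| Cohort | CBC days | Counts | Gaps (days) |
|---|---|---|---|
| Dose finding, Cycles 1-2 | C1 D1, D8, D15, D22; C2 D1, D15 | 6 | 7, 7, 7, 7, 14, 14 |
| Expansion, Cycles 4-5 | C4 D1, D8, D15; C5 D1 | 4 | 7, 7, 14, 28 |

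Each row of gaps sums to 56 days. The visit windows of ±3 days shift the gaps slightly.

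**Step 2: share seen within 7 days of onset.** Assumptions: onset is uniform over the 56 days, only scheduled counts are made, and episodes last 7 days or more. The documents give no episode length. Share = sum of min(7, gap) / 56.

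- Dose finding: 6 × 7 / 56 = 42/56 = 75%.
- Expansion: 4 × 7 / 56 = 28/56 = 50%.

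**Step 3: mean wait from onset to the next scheduled count.** Mean wait = sum of gap² / (2 × 56).

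- Dose finding: (4 × 49 + 2 × 196) / 112 = 588/112 = 5.25 days; longest 14.
- Expansion: (49 + 49 + 196 + 784) / 112 = 1078/112 = 9.6 days; longest 28.

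**Step 4: share ever seen, by episode length d.** Share = sum of min(d, gap) / 56.

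| d (days) | Dose finding | Expansion |
|---|---|---|
| 7 | 75% | 50% |
| 10 | 86% | 61% |
| 14 | 100% | 75% |
| 21 | 100% | 87.5% |
| 28 | 100% | 100% |

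**Step 5: effect of added counts in expansion.**

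- C4 D22 alone (gaps 7, 7, 7, 7, 28): 35/56 = 62.5% within 7 days; mean wait 980/112 = 8.75 days; longest 28.
- C5 D15 alone (gaps 7, 7, 14, 14, 14): 35/56 = 62.5%; mean wait 686/112 = 6.1 days; longest 14.
- Both: the dose-finding pattern, 75%, 5.25 days and 14 days.

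**Step 6: does dated text elsewhere fill the gap?** It does not, for a patient with no known grade 3 cytopenia.

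- Table 3A's weekly CBC follows an observed event.
- Sections 7.4.4.2 and 7.4.5 ask for close or frequent monitoring but name no day.
- Section 5.2.7 allows unscheduled draws when a concern arises.
- The 8- and 24-hour CBCs in 7.4.1.3 are for hospitalized patients, timed to the venetoclax dose.
- The at-risk labs in 4.2.4 end on Day 15.

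**The case against.** The strongest reply is that the comparison is selective. Over Cycles 1-5, expansion patients have more scheduled CBCs than dose-finding patients: 4 + 2 + 1 + 3 + 1 = 11 against 4 + 2 + 1 + 1 + 1 = 9. In Cycles 4-5 alone they have 4 against 2. A reader might infer from the gap after loading that expansion is less closely monitored overall, and these totals do not support that. Dose-finding Cycle 1 is also the DLT window, which expansion Cycle 4 is not, and 28-day intervals are the protocol's norm later on the triplet.

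This stands as a limit on the point, but it does not explain the missing Day 22 count. Cycle 2 Day 15 lies outside the DLT window, and expansion Cycle 1 has weekly assessment with no DLT evaluation. The issue is where the counts fall relative to the first obinutuzumab cycle.

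A second reply is that dosing is already gated. Each infusion and each CC-486 course in Cycles 4-5 follows a count reviewed that day, so an added draw can stop only venetoclax. Patients with an earlier grade 3 cytopenia come under Table 3A, and the dose-modification section is due for review before expansion (4.2.5, 6.2.2). All of this is true. It confines the benefit to first, symptom-free events.

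A third reply concerns size. Counting only the 42 days after the third infusion would give 28/42 = 67% against 14/42 = 33%, but that leaves out the 14 days in which the schedules match; 75% against 50% is the fairer figure. A reader might also take the loss as an upper bound. It is not one: investigator-ordered counts would shrink it, while non-uniform onset could make it larger or smaller. The documents give no per-cycle risk for this triplet, so a number of missed episodes cannot be supported.

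On the TLS labs, 4.2.4 can be read as a specific rule that overrides the general default in 7.4.1.1. That is the sensible reading, but neither section says so and the schedule omits the day.

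**Conclusion.** The point on counts holds as a cheap improvement, with medium confidence. The schedule does not put 7.4.5 into effect in the one expansion cycle where it matters most. Over the first two triplet cycles, 50% of episodes lasting 7 days or more would be seen within 7 days of onset, against 75% in dose finding. The assumptions are uniform onset and scheduled counts only. The figures illustrate the difference; they do not bound it.

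A reader might infer that the trial's conclusions are at risk. The documents do not support that. The DLT window is dose-finding Cycle 1, the RP2D is set there, and the primary expansion endpoint is PET-based. The grade 3/4 AE rate is a listed endpoint of dose finding only (2.7), and no comparison of AE rates between cohorts is planned. An event that goes undetected is not a breach of AESI reporting.

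The Day 2 TLS labs are wrong as written. Section 4.2.4 asks for them in at-risk patients, 7.4.1.1 says post-dose labs are not required, and 5.5.4 and Appendix A omit the day. This rests on the text alone.

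**What to change.** **Counts (expansion only).** Add a draw-only CBC with differential on Cycle 4 Day 22 in 5.5.4 and Appendix A. This follows the dose-finding pattern for the first triplet cycle. As an option, add the same on Cycle 5 Day 15 in 5.6.4 and Appendix A, which cuts the longest gap from 28 to 14 days.

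**Cost.**

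- About 26 to 32 draws per added time point. This assumes that 0 to 6 dose-finding patients treated at the RP2D count toward the 32 (6.2.2).
- By Day 15 or 22 the CC-486 course (Days 1-14) is over and no obinutuzumab is due. A hold would stop venetoclax for up to 7 days of the cycle from Day 22, or up to 14 from Day 15. It would stop nothing in patients already reduced to Days 1-10. Some of these episodes would have resolved without a hold.
- A first neutropenia or thrombocytopenia resumes at the same dose, and a first anemia is transfused. A recurrence could mean a venetoclax and/or CC-486 reduction before the Cycle 7 PET. Whether that is permanent is unclear, because 4.2.5 bars re-escalation while 4.2.2 and 4.2.3 allow it. The review planned before expansion should settle this too.

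**TLS labs.** State in 7.4.1.1 that the Day 2 labs of 4.2.4 are required for at-risk patients, and enter Cycle 4 Day 2 in 5.5.4 and Appendix A for those patients only. The cost is one draw per at-risk patient.
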